17.2 Definition of analysis sets

All dosed patients will be included in the Full Analysis Set (FAS) as well as in the Safety Analysis Set (SAS).

17.3 Primary endpoint

The primary endpoint is the number of bleeding episodes during at least 24 weeks from treatment onset.

The primary endpoint will be estimated using negative binomial regression with log of *exposure time in main phase* as offset, providing an actual estimate of the ABR as well as a corresponding 95% confidence interval.

This analysis has the underlying assumption that the missing data mechanism is “missing at random”, i.e. MAR. Under this assumption, the statistical behaviour of the missing data (given the observed responses and the mean value structure) is assumed to be the same as for the observed data. The endpoint will be estimated based on the full analysis set (FAS) and only data collected prior to discontinuation of trial product or initiation of alternative treatment options will be used to draw inference.

17.4 Sensitivity analyses

To evaluate the robustness of the MAR assumption implied in the primary analysis, a modified tipping point analysis will be performed where patients having discontinued before finalization of the main part are assumed to have a worse outcome compared to what was observed during the main part of the trial. This will be done by adding a value Δ_i to the observed bleeding episodes in the main part of the trial before analysing the data. The offset is maintained as being the exposure during the main phase since it is not possible to identify the amount of missing observation time. The degree of worsening, Δ_i , will gradually be increased to evaluate at which point the upper 95% confidence limit of the prophylactic concizumab ABR is no longer below a threshold of 12.

Protocol
 Trial ID:NN7415-4255
 UTN:U1111-1179-3872
 EudraCT no.:2016-000614-29

~~CONFIDENTIAL~~

Date:	28 December 2017	Novo Nordisk
Version:	4.0	
Status:	Final	
Page:	102 of 124	

The results of the primary analysis will be considered robust if the tipping point is above what is considered clinical plausible.

17.5 Additional analyses

An additional evaluation of the primary endpoint will be made, including actual concizumab dose level as *additional factor in the primary analysis model specified above*. Point estimates and 95% confidence interval will be provided for the ABR at the different dose levels of concizumab (0.15, 0.20 and 0.25 mg/kg). Furthermore, an analysis with individual steady state PK/PD assessments included as covariates in the negative *binomial regression model as specified for the primary analysis* will be performed in order to evaluate possible associations between PK/PD and ABR that potentially could guide dose-selection. The referred steady-state PK/PD assessments comprise the concizumab trough level, maximum plasma concentration (C_{max}) of concizumab, TFPI value prior to the last s.c. dose administration, peak thrombin generation (nM), Endogenous thrombin potential (nM*min) and velocity index (nM/min).

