Daily dosing with 0.15 mg/kg aims to ensure steady-state levels of concizumab plasma concentrations above 100 ng/mL for the majority of the patients starting on this dose. The PK results from explorer^{TM3} showed exposure-response in terms of fewer bleeding episodes recorded for patients who reached plasma concentrations of concizumab above 100 ng/mL see [Figure 3-1](#). The minority of patients which are predicted to have steady-state plasma concentrations below this threshold are expected to experience bleeding episodes and therefore will have the opportunity to be dose-escalated to the dose of 0.2 mg/kg. A further dose escalation to 0.25 mg/kg per day is permitted, again based on the bleeding rate, see section [5.3.1](#).

Protocol
 Trial ID:NN7415-4255
 UTN:U1111-1179-3872
 EudraCT no.:2016-000614-29

~~CONFIDENTIAL~~

Date: 28 August 2018
 Version: 5.0
 Status: Final
 Page: 32 of 127

Novo Nordisk

Figure 5–2 Individual predicted concizumab concentration profiles for all concizumab-treated patients in explorerTM2 (n=4 patients) and explorerTM3 (n=18 patients). The horizontal lines indicate 100 ng/mL, and the shaded areas represent the full range (min-max) of the individual predicted profiles¹.

Due to the high between-patient variability in concizumab concentration observed in explorerTM3, a significant overlap in plasma concentrations of concizumab in patients who received 0.25, 0.5 and 0.8 mg/kg doses was seen, see [Figure 5–2](#). Therefore, choosing three doses that would lead to reasonably distinct mean plasma concentrations of concizumab, and thus different efficacy at each dose level was not deemed possible. For this reason, a traditional parallel arm design was not chosen for the phase 2 trials. In contrast, the titration trial design allows patients to start on a low dose, which is expected to ensure prophylaxis but not marked changes in coagulation parameters, for the majority of patients. Escalation to the next dose level will only occur in the case of lack of efficacy (≥ 3 spontaneous bleeding episodes within the preceding 12 weeks). In addition, the PK of concizumab is heavily influenced by target mediated drug disposition, which means that small differences in concizumab dose ultimately leads to large differences in plasma concentrations. Therefore, daily dosing is proposed for the phase 2 trial, explorerTM5. Daily dosing will allow for the increase in trough levels and thus better efficacy may be expected with a lower dose.

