5.3.1 Dose escalation

Bleeding episodes will be assessed during the trial both at scheduled visits and also between visits. The first 2 weeks of the treatment with concizumab 0.15 mg/kg is considered as a run-in period. Hence the bleeding episodes occurring during the first 2 weeks should not influence a dose escalation decision.

All spontaneous bleeding episodes (sBEs) are counted from 2 weeks after visit 2 (first-dose visit) until visit 16 (end-of-treatment visit), i.e. a total of up to 124 weeks. Dose-escalation will be based on the number of spontaneous, treated bleeding episodes in patients within preceding 12 weeks. However, before dose-escalation can occur, to ensure the safety of the patients, the investigator must take into account the full clinical picture the patient is presenting with and all available laboratory results, including coagulation parameters.

Dose 0.15 mg/kg:

When a sBE occurs, the investigator will determine if ≥ 3 sBEs have occurred within the preceding 12 weeks since visit 2+2weeks (including the current sBE). If yes, and if investigator deems it safe, the patient will have to be dose escalated from 0.15 to 0.20 mg/kg at the next scheduled visit. If the investigator judges that this visit is scheduled too late, he/she should contact the patient for an unscheduled visit.

Dose 0.20 mg/kg:

When an sBE occurs, the investigator will determine if ≥ 3 sBEs have occurred within the preceding 12 weeks (including the current sBE), counting only new sBEs from the beginning of the 0.20 mg/kg treatment period. If yes, and if investigator deems it safe, the patient will have to be dose escalated from 0.20 to 0.25 mg/kg at the next scheduled visit. If the investigator judges that this visit is scheduled too late, he/she should contact the patient for an unscheduled visit.

Dose 0.25 mg/kg:

Patients are not dose escalated further regardless of the number of sBEs. When an sBE occurs, the investigator will determine if ≥ 3 sBEs have occurred within the preceding 12 weeks (including the current sBE), counting only the new sBEs from the beginning of the 0,25mg/kg treatment period. If yes, then the patient must be discontinued from treatment due to lack of efficacy, see Section [6.4](#).

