8.2.4 Details of Haemophilia, Haemophilia Treatment and Bleed History

All available information on haemophilia, prior to screening should be recorded in the eCRF.

- Diagnosis of haemophilia (date)
- Classification of haemophilia type (haemophilia A)
- Severity of haemophilia (severe, moderate or mild)
- Etiology of haemophilia (congenital or acquired)
- Family history of haemophilia [yes or no in eCRF]
- Family history of Prothrombotic disorders [yes or no in eCRF]
- Family history of Thromboembolism [yes or no in eCRF]
- Family history of inhibitors [yes or no in eCRF]
- Deficiency factor level

The following information on bleeding episodes one year prior to screening should be recorded in the eCRF:

- Type of treatment
 - Prophylaxis or on-demand
 - Start date
 - Stop date
- Number of bleeding episodes
 - If possible specify number of spontaneous bleeding episodes.
- Coagulation factor product(s)
 - Brand name, or if the brand is not known, the type of product, (plasma derived or recombinant)
- Dosage used for prophylaxis (for prophylaxis patients only)
- Dosing frequency during prophylaxis (only for prophylaxis patients)
- Approximate dose to treat a bleeding episode
- Approximate number of doses to treat a bleeding episode
- Target joint listing (definition: a target joint is a joint in which 3 or more spontaneous bleeding episodes have occurred within a consecutive 6-month period)
 - Location

Protocol
 Trial ID:NN7415-4255
 UTN:U1111-1179-3872
 EudraCT no.:2016-000614-29

~~CONFIDENTIAL~~

Date: 28 August 2018
 Version: 5.0
 Status: Final
 Page: 56 of 127

Novo Nordisk

- Position (left/right)
- Number of bleeding episodes

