17.3 Primary endpoint

The primary endpoint is the number of bleeding episodes during at least 24 weeks from treatment onset. All treated bleeding episodes will be considered for this endpoint, including bleeding episodes recorded as post-surgical or caused by surgery or other medical for dental procedures.

The primary endpoint will be estimated using negative binomial regression with log of exposure time (the included observational period of the main part) as offset, providing an actual estimate of the ABR as well as a corresponding 95% confidence interval. The offset for first CPoC criterion is the log of the individual exposure time at the last dose level reached at the time of analysis excluding the 2 weeks run-in period for subjects on 0.15 mg/kg. The offset for the second criterion is the log of the individual exposure time in the main part.

This analysis has the underlying assumption that the missing data mechanism is “missing at random”, i.e. MAR. Under this assumption, the statistical behaviour of the missing data (given the observed responses and the mean value structure) is assumed to be the same as for the observed data. The endpoint will be estimated based on the full analysis set (FAS) and only data collected

Protocol
 Trial ID:NN7415-4255
 UTN:U1111-1179-3872
 EudraCT no.:2016-000614-29

~~CONFIDENTIAL~~

Date: 28 August 2018
 Version: 5.0
 Status: Final
 Page: 105 of 127

Novo Nordisk

prior to discontinuation of trial product or initiation of alternative treatment options will be used to draw inference.

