17.5 Additional analyses

An additional evaluation of the primary endpoint will be made, including actual concizumab dose level (interpreted as the patient's last dose level) as *additional factor in the primary analysis model specified above*. Point estimates and 95% confidence interval will be provided for the ABR at the different dose levels of concizumab (0.15, 0.20 and 0.25 mg/kg). Furthermore, a series of analyses with individual steady state PK/PD assessments included as covariates in the negative binomial regression model as specified for the primary analysis will be performed in order to evaluate possible associations between PK/PD and ABR that potentially could guide dose-selection. The referred steady-state PK/PD assessments comprise the concizumab trough level, maximum plasma concentration (C_{max}) of concizumab, TFPI value prior to the last s.c. dose administration, peak thrombin generation (nM), Endogenous thrombin potential (nM*min) and velocity index (nM/min).

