17.8 Interim analysis

The trial does not include a formal interim analysis. However, the split of the trial into a main and extension part offers the opportunity of reporting results before the end of the trial. Other reporting of the trial might be done during the extension part once the data collection and review of the main part data has been finalised and individual clinical study reports might in such case be issued. A final clinical study report describing results from the main and extension part will be written when the last patient has either completed or withdrawn from the trial.

All main conclusions regarding clinical proof of concept and dose guidance for phase 3 will be based on the reporting after the main part, see [Figure 17-1](#).

[figure not shown]

Figure 17-1 Definition of main and extension part

Protocol
 Trial ID:NN7415-4255
 UTN:U1111-1179-3872
 EudraCT no.:2016-000614-29

~~CONFIDENTIAL~~

Date: 28 August 2018
 Version: 5.0
 Status: Final
 Page: 110 of 127

Novo Nordisk

18 Ethics

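### The PK/PD–ABR models meant to inform dose selection leave out pre-trial bleeding and regimen, so bleeding-driven titration biases their slope against benefit

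*Protocol*

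**What the plan says.** Section 17.5 of the current protocol (version 5.0) plans a series of models with "individual steady state PK/PD assessments included as covariates in the negative binomial regression model as specified for the primary analysis". It also states their purpose: the analyses "will be performed in order to evaluate possible associations between PK/PD and ABR that potentially could guide dose-selection". The PK/PD values are the concizumab trough and maximum concentration, TFPI before the last dose, and three thrombin-generation measures. The base model is given in section 17.3: "The primary endpoint will be estimated using negative binomial regression with log of exposure time (the included observational period of the main part) as offset". It has an intercept and an offset and nothing else.

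Section 17.8 gives the use of the results: "All main conclusions regarding clinical proof of concept and dose guidance for phase 3 will be based on the reporting after the main part".

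On titration, section 5.2 says: "Escalation to the next dose level will only occur in the case of lack of efficacy". Section 5.3.1 sets the trigger at three or more spontaneous treated bleeds in a 12-week window. If that count is reached on the top level, "then the patient must be discontinued from treatment due to lack of efficacy".

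On history, section 8.2.4 says that "information on bleeding episodes one year prior to screening should be recorded in the eCRF". The same list records whether the patient was on prophylaxis or on-demand treatment. No efficacy model in section 17 uses either item.

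**The concern.** Exposure in this trial is partly assigned by the outcome. A patient with a high bleeding tendency is moved up, and so has a higher concentration, lower free TFPI and higher thrombin generation when these values are set against his ABR. Bleeding tendency is then a common cause of exposure and ABR, and it pushes the slope towards more bleeding at higher exposure. Using the right concentration for the right period does not remove this.

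Tendency is likely to vary widely. On-demand and prophylaxis patients are mixed (section 5.1), only on-demand patients need a minimum bleed count (section 6.2), and the sample size assumes an over-dispersion of 6 (section 17.1). Section 17 warns of potential bias for the end-dose proof-of-concept criterion but not for these models. At stake is an exposure–response estimate that understates, or misses, a real effect when the phase 3 dose is discussed.

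**Working it through.** **1. The plan's own figure.** The protocol gives no figure for the exposure slope, so the check starts from the power of the same model in Table 17-1. Power = Φ(ln(12/ABR) / √(OD/(n·ABR·T)) − 1.96). With ABR 4, OD 6, n = 30 and T = 0.5 years: ln 3 = 1.099, √(6/60) = 0.316, 1.099/0.316 − 1.96 = 1.51, so power is 93.5%. Negative binomial simulation gives 95.5%. The stated 95% is reproduced.

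**2. Heterogeneity.** With mean count 4 × 0.5 = 2 and OD = 1 + 2/shape, an OD of 6 gives gamma shape 2/5 = 0.4. The 24-week range of 3–5 quoted from prior trials in section 17.1 gives shape 1.0 to 0.5.

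**3. Inputs.**
- From the protocol: the titration rule, including stopping at the top level. Typical exposure at the three levels, relative to 0.8 mg/kg every fourth day, is about 25% and below 40% and 70% (section 5.2, footnote), taken as ratios 1 : 1.6 : 2.8.
- Assumed, because the protocol says only that PK variability is high and the dose response rather steep: PK spread, slope, 70% of bleeds spontaneous, and half of patients on prior prophylaxis.

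**4. Trials of 33 patients, last-dose data.** Settings: follow-up 24–41 weeks; untreated rate lognormal, mean 30/year, log-SD 0.9; concentration at the starting level median 150 ng/mL, log-SD 0.8, independent of bleeding tendency; history of a prophylaxis patient set to one quarter of his untreated rate; true log-concentration slope -1. About a third of patients escalate, and the last-dose ABR is 4.3 to 4.6.
- Unadjusted median: -0.47 to -0.52 over repeat runs, significant in 53–54% of trials.
- Adjusted for log bleed history and regimen: -0.79 to -0.85; with error added to the history, -0.71 to -0.74.
- Narrower PK spread: unadjusted about -0.3.
- Steeper slopes: -1.5 gives -0.94 (0.94/1.5 = 63% kept); -2 gives -1.41 (1.41/2 = 71% kept).
- Wrong sign, unadjusted: 2–6% of trials in these settings, up to 23% with narrower PK spread.

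**5. Wider range.** Share of the true slope kept on last-dose data, unadjusted / adjusted. Settings: 300 patients per run, 8 months, gamma tendency, base rate 6/year; history scaled from 30/year (on-demand) and 6.5/year (prophylaxis), the two rates cited in section 17.

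| Shape (OD at mean 2) | True slope | PK CV 0.6 | PK CV 1.0 |
|---|---|---|---|
| 5 (1.4) | -1 | 0.62 / 0.72 | 0.72 / 0.77 |
| 5 | -3 | 0.72 / 0.79 | 0.89 / 0.94 |
| 1.0 (3) | -1 | 0.28 / 0.74 | 0.55 / 0.86 |
| 1.0 | -3 | 0.52 / 0.81 | 0.81 / 0.97 |
| 0.4 (6) | -1 | -0.30 / 0.83 | 0.30 / 0.94 |
| 0.4 | -3 | 0.33 / 0.84 | 0.60 / 0.91 |

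A negative share means a reversed slope. Step 4 fits this table: log-SD 0.8 is a CV of √(e^0.64 − 1) = 0.95, and log-SD 0.9 matches shape 1/(e^0.81 − 1) = 0.80.

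**6. Cause.** With titration switched off, the unadjusted model keeps 0.98 to 1.08 of the slope. The bias therefore comes from titration.

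**7. No true effect.** With rates scaled to an ABR of about 4, the planning value, a significant positive slope appears in about 12–27% of trials unadjusted and 4–7% adjusted.

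**8. Limit of the adjustment.** If the bleed history of prophylaxis patients says nothing about their tendency (shape 0.6, slopes -0.6 to -2), the adjusted model keeps -0.33 to 0.69, against -0.57 to 0.63 unadjusted.

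**The case against.** The strongest reply has four parts.

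- **Weight.** These are additional, exploratory models, and section 17.8 rests dose guidance on the whole main-part report, which also holds PK, PD and coagulation summaries. This stands: the models are one input, and no confirmatory claim is touched.
- **SAP.** Baseline covariates for such an analysis are often settled in a statistical analysis plan, which is not at hand. This carries less weight, because section 17.5 names the model: the values are "included as covariates in the negative binomial regression model as specified for the primary analysis will be performed".
- **Who is escalated.** Section 5.2 expects mainly patients with low concentrations to bleed and be moved up. The simulations already include PK variation independent of tendency, and the bias remains.
- **Size.** Slope, PK spread and heterogeneity are assumed. This stands.

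A reader might infer that a real effect will generally be halved or reversed. The documents do not support that. A typical reversal needs strong heterogeneity or narrow PK spread. The shape of 0.4 also assigns the whole over-dispersion of 6 to bleeding tendency, although in a model without covariates that figure already includes variation due to exposure.

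A reader might also infer that, with no effect, most trials would show a false harmful slope. Rates of 61–64% do arise if the untreated rate stays at 30/year, but the last-dose ABR is then about 15 with about 75% of patients escalated. Such a drug would miss the criterion of 12, and little dose guidance would be left to distort.

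**Conclusion.** The point holds in conditional form. The protocol fixes an exposure–ABR model whose slope is confounded by bleeding tendency through the titration rule, and it leaves out two recorded baseline variables that reduce the confounding. The direction is against benefit. With a true slope of -1 the unadjusted estimate is typically about half of the truth or somewhat less; with a steeper slope about 60–70% is kept; with little heterogeneity, or a very steep slope and wide PK spread, the loss is only about 10–40%. Confidence is high in the direction and moderate in the size. Adjustment helps but does not remove the bias.

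**What to change.** In section 17.5, add log(pre-trial annual bleed count + 0.5) and pre-trial regimen (on-demand or prophylaxis) as covariates in each PK/PD–ABR model. Report the adjusted and unadjusted slopes side by side, with the adjusted slope leading for dose guidance. Add a statement that the adjustment is partial, because a prophylaxis patient's history reflects treated bleeding, so some bias against benefit remains.

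The cost is one or two sentences and no new data. The downside is two more model terms with about 33 patients, and regimen-only adjustment where no bleed count is documented. Trial conduct and the proof-of-concept test do not change.

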17.6 Secondary endpoints

17.6.1 Supportive secondary efficacy endpoints

- The number of bleeding episodes during 76 weeks from treatment onset.
- The number of spontaneous bleeding episodes during at least 24 weeks from treatment onset.
- The number of spontaneous bleeding episodes during 76 weeks from treatment onset.

The supportive secondary endpoints will be estimated using the same negative binomial regression model as the primary endpoint.

17.6.2 Supportive secondary safety endpoints

- Number of treatment-emergent adverse events (TEAEs) during at least 24 weeks from treatment onset
- Number of TEAEs during 76 weeks from treatment onset.
- Occurrence of anti-concizumab antibodies during at least 24 weeks from treatment onset.
- Occurrence of anti-concizumab antibodies during 76 weeks from treatment onset.
- Change from baseline of fibrinogen during 24 weeks from treatment onset.
- Change from baseline of fibrinogen during 76 weeks from treatment onset.

Protocol
 Trial ID:NN7415-4255
 UTN:U1111-1179-3872
 EudraCT no.:2016-000614-29

~~CONFIDENTIAL~~

Date: 28 December 2017
 Version: 4.0
 Status: Final
 Page: 103 of 124

Novo Nordisk

- Change from baseline of D-dimer during 24 weeks from treatment onset.
- Change from baseline of D-dimer during 76 weeks from treatment onset
- Change from baseline of prothrombin fragment 1 + 2 (F1 + 2) during 24 weeks from treatment onset.
- Change from baseline of F1 + 2 during 76 weeks from treatment onset.
- Change from baseline of prothrombin time (PT) during 24 weeks from treatment onset.
- Change from baseline of PT during 76 weeks from treatment onset.
- Change from baseline of activated partial thromboplastin time (APTT) during 24 weeks from treatment onset.
- Change from baseline of APTT during 76 weeks from treatment onset.
- Change from baseline of antithrombin (AT) during 24 weeks from treatment onset.
- Change from baseline of AT 76 weeks from treatment onset.

Adverse Events will be coded using the most recent version of Medical Dictionary for Regulatory Activities (MedDRA) coding.

A Treatment Emergent Adverse Event (TEAE) is defined as an event that has onset from the first exposure to treatment until the last visit in the trial. Treatment-emergent adverse event endpoints will be summarised by system organ class, preferred term, seriousness, severity and relation to trial product. All Adverse events will further be listed.

Frequency of binding anti-concizumab antibodies will be listed and summarised by time frame according to the two endpoint definitions.

All laboratory safety endpoints will be plotted by time, both as absolute values and change from baseline. Laboratory safety endpoints will further be summarised and listed.

